Patients are expected to remain in the clinic for the completion of all procedures (\sim 8:00 a.m. to \sim 12:00 p.m.); however, at the discretion of the investigator, patients will be permitted to leave the clinic following the completion of the dosing.

5.3.4. Patient Instructions, Cohort 1

Before patients leave the clinic, they should receive an appointment for their next study visit and the following instructions:

- Remember to use TRAVATAN Z once daily in the evening (as close to 8:00 p.m. as you can) in the eye that is NOT having cataract surgery. DO NOT PUT TRAVATAN Z in the eye that had the ENV515 implant(s). Continue using TRAVATAN Z only through Day 24, one day prior to Visit 8 (Day 25 ± 1 day). Please remember to bring TRAVATAN Z with you to Visit 8 (Day 25 ± 1 day) so that it can be collected from you.
- Continue to withhold (not use) all your other eye drop medications until the end of the study (if appropriate). With your doctor's approval, you may be able to use artificial tear eye drops.
- Remember not to use alcohol or tobacco products within 8 hours of your next clinic visit.
- Call your study site if you have any problems.
- Please avoid physical activities associated with jarring physical motions, such as horseback riding, for the rest of the study.

5.4. Visit 4/Day 3 ± 1 Day/Treatment Period, Cohort 1

Query patient about changes in concomitant medications and whether or not they have experienced symptoms suggesting an AE. AEs will be documented.

Assessments will be conducted in the following order. Both eyes will be evaluated at all ophthalmic assessments:

- 1. Assess BCVA (ETDRS) with manifest refraction
 - If dilation is required to properly conduct BCVA (ETDRS) with manifest refraction the assessment should be performed after the slit lamp biomicroscopy and IOP measurement.
- 2. Perform slit lamp biomicroscopy
- 3. Perform corneal staining
- 4. Measure IOP at 8:00 a.m. (±30 minutes)
- 5. Perform gonioscopy
- 6. Perform anterior chamber OCT

Patients are expected to remain in the clinic for the completion of all procedures (\sim 8:00 a.m. to \sim 10:00 a.m.). Before patients leave the clinic, they should receive an appointment for their next study visit and the instructions provided in Section 5.3.4.

5.5. Visit 5/Day 7 ± 1 Day/Treatment Period, Cohort 1

Query patient about changes in concomitant medications and whether or not they have experienced symptoms suggesting an AE. AEs will be documented.

Assessments will be conducted in the following order. Both eyes will be evaluated at all ophthalmic assessments:

- 1. Assess BCVA (ETDRS) with manifest refraction
 - If dilation is required to properly conduct BCVA (ETDRS) with manifest refraction the assessment should be performed after the slit lamp biomicroscopy and IOP measurement.
- 2. Perform slit lamp biomicroscopy
- 3. Perform corneal staining
- 4. Measure IOP at 8:00 a.m. (±30 minutes)

Patients are expected to remain in the clinic for the completion of all procedures (\sim 8:00 a.m. to \sim 9:00 a.m.). Before patients leave the clinic, they should receive an appointment for their next study visit and the instructions provided in Section 5.1.2.

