 - Non-contact specular microscopy can be performed anytime during the clinic visit and does not need to follow the order as written.
- 12. Assess VF
- 13. Perform anterior chamber OCT
- 14. Perform dilated funduscopic exam
- 15. Perform physical examination (can be performed anytime during the site visit and does not need to follow the order as written)

- 16. Assess vital signs (can be performed anytime during the site visit and does not need to follow the order as written)
- 17. Collect non-fasting blood and urine for clinical laboratory tests
- 18. If female of childbearing potential, perform urine or serum pregnancy test
- 19. Verify that patient meets all applicable entry criteria
- 20. Query patient about whether or not they have experienced symptoms suggesting an AE. AEs will be documented

At the end of the examination, patients will be asked to discontinue their current glaucoma medication(s). Section 16.2.2 references the duration of the washout period given different types of topical glaucoma therapy. The patient will be asked to return for the baseline visit after 4 weeks. The washout period may be extended up to 2 weeks, if it remains safe for the patient, to accommodate the patient's or the investigator's schedule.

5.1.2. Patient Instructions, Cohort 1

Before patients leave the clinic, they should receive an appointment for their next study visit and the following instructions:

- Discontinue use of all eye drop medications until the end of the study (if appropriate). With your doctor's approval, you may be able to use artificial tear eye drops.
- Remember not to use alcohol or tobacco products within 8 hours of your next clinic visit.
- At Visits 2 and 8, be prepared for a long clinic visit. You will be expected to have IOP measurements at 8:00 a.m., 10:00 a.m., and 4:00 p.m. You may leave the clinic after the 10:00 a.m. assessments, with your doctor's approval.
- Call your study site if you have any problems.
- Remember not to wear contact lenses 2 days for soft contact lenses and 7 days for RGP lenses prior to next visit

5.2. Visit 2/Day -7 to -1/Baseline, Cohort 1

Patients will be queried about changes in medications and whether or not they have experienced symptoms suggesting an AE. AEs will be documented.

5.2.1. **Baseline Assessments, Cohort 1**

Assessments will be conducted in the following general order. Both eyes will be evaluated at all ophthalmic assessments:

- 1. Assess BCVA (ETDRS) with manifest refraction

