5.6. Visit $6/\text{Day } 14 \pm 1 \text{ Day/Treatment Period, Cohort } 1$

Query patient about changes in concomitant medications and whether or not they have experienced symptoms suggesting an AE. AEs will be documented.

Assessments will be conducted in the following order. Both eyes will be evaluated at all ophthalmic assessments:

- 1. Assess BCVA (ETDRS) with manifest refraction
 - If dilation is required to properly conduct BCVA (ETDRS) with manifest refraction the assessment should be performed after the slit lamp biomicroscopy and IOP measurement.
- 2. Perform pupil measurement
- 3. Perform slit lamp biomicroscopy
- 4. Perform corneal staining
- 5. Measure IOP at 8:00 a.m. (±30 minutes)
- 6. Perform gonioscopy
- 7. Perform pachymetry (contact)
- 8. Perform specular microscopy (non-contact)
 - Non-contact specular microscopy can be performed anytime during the site visit and does not need to follow the order as written.
- 9. Perform anterior chamber OCT
- 10. Perform dilated funduscopic exam
- 11. Collect non-fasting blood and urine for clinical laboratory tests and systemic PK

Patients are expected to remain in the clinic for the completion of all procedures (\sim 8:00 a.m. to \sim 10:00 a.m.). Before patients leave the clinic, they should receive an appointment for their next study visit and the instructions provided in Section 5.3.4.

5.7. Visit 7/Day 21 ± 1 Day/Treatment Period, Cohort 1

Query patient about changes in concomitant medications and whether or not they have experienced symptoms suggesting an AE. AEs will be documented.

Assessments will be conducted in the following order. Both eyes will be evaluated at all ophthalmic assessments:

- 1. Assess BCVA (ETDRS) with manifest refraction
 - If dilation is required to properly conduct BCVA (ETDRS) with manifest refraction the assessment should be performed after the slit lamp biomicroscopy and IOP measurement.
- 2. Perform slit lamp biomicroscopy
- 3. Perform corneal staining

- 4. Measure IOP at 8:00 a.m. (±30 minutes)
- 5. Perform gonioscopy

Patients are expected to remain in the clinic for the completion of all procedures (\sim 8:00 a.m. to \sim 10:00 a.m.). Before patients leave the clinic, they should receive an appointment for their next study visit and the instructions provided in Section 5.3.4.

5.8. Visit 8/Day 25 ± 1 Day/Treatment Period, Cohort 1

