5.8.1. Disbursement and First Administration of Pre-Surgical Medications

Following the completion of all assessments, the patients will receive their pre-surgical antiinflammatory and antibiotic medications: PRED FORTE, PROLENSA, and VIGAMOX. The

87

medications will be administered by the patients on Day 26, 27, and 28 twice a day for each medication, once in the morning and once in the evening. Following the removal of the ENV515 implant (Visit 9/Day 28), it is upon the discretion of the investigator to determine the post-operative medication regimen. Patients will be provided with instructions on use of these medications and what to do to prepare for their cataract surgery.

Patients are expected to remain in the clinic for the completion of all procedures (~8:00 a.m. to ~4:30 p.m.). However, at the discretion of the investigator, patients will be permitted to leave the clinic after completing the 10:00 a.m. IOP measurement and will return to the clinic before the 4:00 p.m. IOP measurement. Any patient that leaves the clinic will be instructed to return no later than 30 minutes prior to 4:00 p.m. Before patients leave the clinic for the day, they should receive an appointment for their next study visit and the instructions provided in Section 5.1.2.

5.9. Visit 9/Day 28/Cataract Surgery, Cohort 1

Query patient about changes in concomitant medications and whether or not they have experienced symptoms suggesting an AE. AEs will be documented.

5.9.1. Pre-surgery Assessment, Cohort 1

Assessments will be conducted in the following order. Both eyes will be evaluated at all ophthalmic assessments:

- 1. Assess BCVA (ETDRS) with manifest refraction
- 2. If dilation is required to properly conduct BCVA (ETDRS) with manifest refraction the assessment should be performed after the slit lamp biomicroscopy and IOP measurement.
- 3. Perform slit lamp biomicroscopy
- 4. Perform corneal staining
- 5. Measure IOP at 8:00 a.m. (±30 minutes)
- 6. Perform gonioscopy to identify the location of the ENV515 implants to facilitate implant recovery during the cataract removal procedure
- 7. Additional assessment needed prior to cataract removal conducted per discretion of the principal investigator

5.9.2. Cataract Removal Procedure Combined with Aqueous Humor Sampling and Implant Recovery, Cohort 1

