- 6. Perform gonioscopy (if gonioscopy images are collected, please conduct the gonioscopy after the 4:00 p.m. IOP measurement)
- 7. Perform pachymetry (contact)
- 8. Perform specular microscopy (non-contact) for both eyes (can be performed anytime during the visit)
- 9. Assess VF
- 10. Perform anterior chamber OCT with the ENV515 implant(s) in the field of view of at least one OCT image
- 11. Measure IOP at 10:00 a.m. (±30 minutes)
- 12. Measure IOP at 4:00 p.m. (±30 minutes)
- 13. Perform dilated funduscopic exam
- 14. Perform body system assessment (can be performed anytime during the site visit)
- 15. Assess vital signs (can be performed anytime during the site visit)
- 16. Collect non-fasting blood and urine for clinical laboratory tests **and** systemic PK (can be performed any time during the site visit)
- 17. If female of childbearing potential, perform urine pregnancy test
- 18. Collect used timolol maleate 0.5% ophthalmic solution bottle
- 19. Complete the exit form
- 20. Discharge the patient from the trial

13. PROCEDURE SCHEDULE BY STUDY VISIT, COHORT 3

At visits with IOP diurnal measurements, patients are expected to remain in the clinic for the completion of all procedures (~7:30 a.m. to ~5:00 p.m.). However, at the discretion of the investigator, patients will be permitted to leave the clinic after completing the 10:00 a.m. IOP measurement and will return to the clinic before the 4:00 p.m. IOP measurement. Any patient that leaves the clinic will be instructed to return no later than 30 minutes prior to the 4:00 p.m. IOP measurement.

Before patients leave the clinic, they should receive an appointment for their next study visit and the instructions provided in Section 13.1.2.

13.1. Visit 1/Day -56 to -42/Screening Evaluation, Cohort 3

At Visit 1, patients will be screened, and if eligible, enrolled into the study. Before any study specific assessments are performed, written informed consent will be obtained from each patient. During the visit, the procedures described below will be performed. These procedures can occur over a seven day window.

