13.5. Visit $5/Day 14 \pm 3 Days/Treatment Period, Cohort 3$

Query patient about changes in concomitant medications and whether or not they have experienced symptoms suggesting an AE. AEs and concomitant medications will be documented.

Assessments will be conducted in the following order. Both eyes will be evaluated at all ophthalmic assessments unless otherwise noted:

- 1. Assess BCVA (ETDRS) with manifest refraction
- 2. Perform pupil measurement
- 3. Perform slit lamp biomicroscopy (if corneal opacity is observed, please collect corneal photograph at each visit until opacity has resolved or patient is exited from the study)
- 4. Perform corneal staining
- 5. Measure IOP at 8:00 a.m. (±30 minutes) Please make sure that timolol maleate 0.5% ophthalmic solution is administered after the IOP measurement.
- 6. Perform gonioscopy (if gonioscopy images are collected, please conduct the gonioscopy after the 4:00 p.m. IOP measurement)
- 7. Perform pachymetry (contact)
- 8. Perform specular microscopy (non-contact) study eye only; Non-contact specular microscopy can be performed anytime during the site visit
- 9. Perform anterior chamber OCT with the ENV515 implant(s) in the field of view of at least one OCT image
- 10. Measure IOP at 10:00 a.m. (±30 minutes)
- 11. Measure IOP at 4:00 p.m. (±30 minutes)
- 12. Collect blood sample for PK analysis. (can be performed after the 10 a.m. IOP)

Before patients leave the clinic, they should receive an appointment for their next study visit and the instructions provided in Section 13.3.4.

13.6. Visit $5a/Day 28 \pm 3 Days/Treatment Period$, Cohort 3

Query patient about changes in concomitant medications and whether or not they have experienced symptoms suggesting an AE. AEs and concomitant medications will be documented.

- 1. Assess BCVA (ETDRS) with manifest refraction
- 2. Perform slit lamp biomicroscopy (If corneal opacity is observed, please collect corneal photograph at each visit until opacity has resolved or patient is exited from the study at selected sites.)
- 3. Perform corneal staining
- 4. Measure IOP at 8:00 a.m. (±30 minutes) Please make sure that timolol maleate 0.5% ophthalmic solution is administered after the IOP measurement.

- 5. Perform gonioscopy (if gonioscopy images are collected, please conduct the gonioscopy after the 4:00 p.m. IOP measurement)
- 6. Perform pachymetry (contact)

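### Cohort 1 Visit 5 (Day 7) gives patients the screening stop-all-drops instructions while they should be using TRAVATAN Z, which exposes the Day 14 between-eye comparison

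*Protocol*

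**What the plan says.** **Cohort 1, TRAVATAN Z period.** Section 5.3.4, given at dosing, tells the patient: "Remember to use TRAVATAN Z once daily in the evening", in the non-study eye, through Day 24. It asks patients to withhold only their *other* drops. Sections 5.4, 5.6 and 5.7 (Visits 4, 6 and 7) send patients home with these same instructions ("study visit and the instructions provided in Section 5.3.4"). Section 5.5 (Visit 5, Day 7) does not: "they should receive an appointment for their next study visit and the instructions provided in Section 5.1.2". Section 5.1.2 was written for the start of washout and reads: "Discontinue use of all eye drop medications until the end of the study (if appropriate"). It mentions artificial tears but not TRAVATAN Z.

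**Cohort 1, around surgery.** Section 5.8.1 (Visit 8) dispenses three pre-surgical drops: "medications will be administered by the patients on Day 26, 27, and 28 twice a day for each medication". It then says that before leaving "for the day, they should receive an appointment for their next study visit and the instructions provided in Section 5.1.2". Section 5.9.3 (Visit 9) also names Section 5.1.2, and next allows IOP-lowering drugs to be prescribed.

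**Cohort 3.** The opening text of Section 13 states generally: "Before patients leave the clinic, they should receive an appointment for their next study visit and the instructions provided in Section 13.1.2". Section 13.1.2 is the Cohort 3 screening text and carries the same stop-all-drops line. The visit sections differ. Section 13.5, for example, says "they should receive an appointment for their next study visit and the instructions provided in Section 13.3.4", and Section 13.3.4 tells patients to use timolol twice daily.

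**Analysis.** Cohort 1 SAP Section 8.3.2 compares the 8 AM change from baseline between study and non-study eyes by paired t-test in each treatment group. Section 7 of each SAP says compliance with the active control will not be collected.

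**The concern.** The fellow eye is the active control. If a patient stops TRAVATAN Z because the Day 7 instructions say to stop all drops, the fellow eye's pressure rises towards its untreated level, but the reading is still analysed as TRAVATAN Z. The fellow eye then shows a smaller fall from baseline, and the between-eye contrast moves in favour of ENV515. Since the SAP plans no use of comparator compliance data, the planned analysis could not show that this had happened.

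For the surgical visits and Cohort 3 the concern is narrower: two parts of the protocol give a patient inconsistent directions about drops.

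**Working it through.** There is no planned figure to reproduce. The check traces each cross-reference to its target and counts the days exposed.

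**Step 1. Cohort 1 post-dose visits that name instructions**

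| Visit (day) | Section | Instructions named | TRAVATAN Z still due? |
|---|---|---|---|
| 4 (3 ± 1) | 5.4 | 5.3.4 | yes |
| 5 (7 ± 1) | 5.5 | 5.1.2 | yes |
| 6 (14 ± 1) | 5.6 | 5.3.4 | yes |
| 7 (21 ± 1) | 5.7 | 5.3.4 | yes |
| 8 (25 ± 1) | 5.8.1 | 5.1.2 | no |
| 9 (28) | 5.9.3 | 5.1.2 | no |
| 10 (33 to 38) | 5.10 | 5.3.4 | no |

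The screening text is named at 3 of 7 visits overall, but at only 1 of the 4 visits where TRAVATAN Z is still to be used.

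**Step 2. Length of the exposed interval.** Visit 5 falls on Day 6 to 8 and Visit 6 on Day 13 to 15, both with morning readings. TRAVATAN Z is taken in the evening.

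- Shortest: 13 − 8 = 5 days, so 5 evening doses missed.
- Planned: 14 − 7 = 7 days.
- Longest: 15 − 6 = 9 days.

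**Step 3. Readings touched.** On-treatment 8 AM comparisons fall on Days 3, 7, 14, 21 and 25. The Day 7 IOP is taken before the patient leaves Visit 5, so the directly exposed reading is Day 14: 1 of 5. Visit 6 then gives Section 5.3.4 again. The interval from Visit 6 to Visit 8 is 24 − 15 = 9 to 26 − 13 = 13 days, with a further reminder at Visit 7. The Day 25 primary endpoint therefore follows two later TRAVATAN Z reminders.

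**Step 4. Number of readings.** Protocol Table 9 gives 7, 10, 2 and 2 patients by dose group, 21 in all. At most 21 fellow-eye Day 14 readings could be affected.

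**Step 5. Cohort 3.** Sections 13.4 to 13.10 cover Visit 4, 5, 5a, 6, 7, 8 to 12 and 13 to 15: 1 + 1 + 1 + 1 + 1 + 5 + 3 = 13 visits in 7 sections. All 7 name Section 13.3.4. Sections 13.12 and 13.14 (the extensions) name Section 12.3.4, also timolol instructions. None of these 9 sections names Section 13.1.2. Only the opening text of Section 13 applies it generally.

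**The case against.** **Patients had other direction.** Section 5.1.2 is qualified by the words if appropriate. Section 16.1 excepts study medication from the rule on stopping glaucoma drugs. Patients heard the TRAVATAN Z instructions at Visits 3, 4, 6 and 7. This makes widespread stopping unlikely, and there is no evidence that anyone stopped. It does not remove the contradiction. Section 5.3.4 carries the same qualifier, but it also has an explicit dosing line and limits withholding to other drops; Section 5.1.2 has neither. Section 16.1 addresses the site and is not part of what the patient is told.

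**The surgical visits do not concern the comparator.** This stands. TRAVATAN Z ends at Day 24 and is collected at Visit 8. Section 5.8.1 also promises separate instructions for the pre-surgical drops and leaves the post-operative regimen to the investigator. What remains is an inconsistency of wording.

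**Cohort 3.** A reader might infer from the opening text of Section 13 that Cohort 3 patients were told at each diurnal visit to stop timolol. The visit sections do not support that: they name timolol instructions throughout, and Sections 13.6 to 13.9 also provide for issuing new bottles. The conflict is between one general sentence and the visit-level text.

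**Size.** A reader might take the 6.6 mmHg fall reported for TRAVATAN Z in Section 1.4.2 as the possible error. That figure is a Day 25 diurnal mean, not a Day 14 8 AM value, and it says nothing about timolol. It would also require the full effect to vanish in 5 to 9 days, whereas the protocol plans a washout of at least 4 weeks (5/28 = 18% to 9/28 = 32% of that).

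**Conclusion.** The contradiction at Cohort 1 Visit 5 is real and lies inside the TRAVATAN Z period. It exposes one of five on-treatment 8 AM between-eye comparisons, Day 14, in at most 21 fellow eyes. Any bias would favour ENV515. Its size cannot be derived from the documents: that would need the number of patients who stopped and the rate at which the effect is lost, and neither is given.

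The affected analysis is exploratory, and Cohort 1 SAP Section 8.2 describes the 8 AM readings outside the diurnal visits as a safety measure. A reader might infer that the Day 25 primary result is compromised. The documents do not support that, provided patients who stopped resumed when given Section 5.3.4 again at Visit 6.

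Visits 8 and 9 and the Section 13 opening text are lesser inconsistencies. Cohort 3 IOP is only summarised by eye, without formal testing (Cohorts 2 and 3 SAP, Sections 8.1 and 10).

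**What to change.** 1. **Reconcile the text.** In Cohort 1, bring Sections 5.1.2, 5.3.4, 5.5, 5.8.1 and 5.9.3 into agreement. In Cohort 3, do the same for the Section 13 opening text with Sections 13.1.2, 13.3.4, 13.4 to 13.10, 13.12 and 13.14. No post-dose visit should give instructions that conflict with the drops required at that visit. Which text should govern is for the sponsor and investigators.

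2. **Use the non-use notes.** Section 16.3 asks sites to record, in the accountability log, source document and eCRF, reported comparator non-use of 5 or more days before a visit. That threshold matches the 5 to 9 day interval. Section 7 of each SAP should be reconciled with this requirement. One limit: Section 16.3 ties the assessment to return of the medication, and Cohort 1 collects TRAVATAN Z only at Visit 8, so a gap between Days 7 and 14 may rest on recall. The documents describe no record of which instructions a patient was given.

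3. **Run one sensitivity summary.** Flag Day 14 fellow-eye readings with such a note and repeat the Day 14 8 AM between-eye summary without them. In the two groups of 2 patients this may leave too few to summarise, and the report should say so. For Cohort 3, flag such readings in the descriptive IOP summary.

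Cohort 1 is complete, so for that cohort only items 2 and 3 can change what is reported. The cost is the cross-reference edits, one record check and one extra summary.

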5.6. Visit $6/\text{Day } 14 \pm 1 \text{ Day/Treatment Period, Cohort } 1$

Query patient about changes in concomitant medications and whether or not they have experienced symptoms suggesting an AE. AEs will be documented.

Assessments will be conducted in the following order. Both eyes will be evaluated at all ophthalmic assessments:

- 1. Assess BCVA (ETDRS) with manifest refraction
 - If dilation is required to properly conduct BCVA (ETDRS) with manifest refraction the assessment should be performed after the slit lamp biomicroscopy and IOP measurement.
- 2. Perform pupil measurement
- 3. Perform slit lamp biomicroscopy
- 4. Perform corneal staining
- 5. Measure IOP at 8:00 a.m. (±30 minutes)
- 6. Perform gonioscopy
- 7. Perform pachymetry (contact)
- 8. Perform specular microscopy (non-contact)
 - Non-contact specular microscopy can be performed anytime during the site visit and does not need to follow the order as written.
- 9. Perform anterior chamber OCT
- 10. Perform dilated funduscopic exam
- 11. Collect non-fasting blood and urine for clinical laboratory tests and systemic PK

Patients are expected to remain in the clinic for the completion of all procedures (\sim 8:00 a.m. to \sim 10:00 a.m.). Before patients leave the clinic, they should receive an appointment for their next study visit and the instructions provided in Section 5.3.4.

5.7. Visit 7/Day 21 ± 1 Day/Treatment Period, Cohort 1

Query patient about changes in concomitant medications and whether or not they have experienced symptoms suggesting an AE. AEs will be documented.

Assessments will be conducted in the following order. Both eyes will be evaluated at all ophthalmic assessments:

- 1. Assess BCVA (ETDRS) with manifest refraction
 - If dilation is required to properly conduct BCVA (ETDRS) with manifest refraction the assessment should be performed after the slit lamp biomicroscopy and IOP measurement.
- 2. Perform slit lamp biomicroscopy
- 3. Perform corneal staining

- 4. Measure IOP at 8:00 a.m. (±30 minutes)
- 5. Perform gonioscopy

Patients are expected to remain in the clinic for the completion of all procedures (\sim 8:00 a.m. to \sim 10:00 a.m.). Before patients leave the clinic, they should receive an appointment for their next study visit and the instructions provided in Section 5.3.4.

5.8. Visit 8/Day 25 ± 1 Day/Treatment Period, Cohort 1

Query patient about changes in concomitant medications and whether or not they have experienced symptoms suggesting an AE. AEs will be documented. Collect TRAVATAN Z from the patient.

Assessments will be conducted in the following order. Both eyes will be evaluated at all ophthalmic assessments:

- 1. Assess BCVA (ETDRS) with manifest refraction
 - If dilation is required to properly conduct BCVA (ETDRS) with manifest refraction the assessment should be performed after the slit lamp biomicroscopy and IOP measurement.
- 2. Perform pupil measurement
- 3. Perform slit lamp biomicroscopy
- 4. Perform corneal staining
- 5. Measure IOP at 8:00 a.m. (±30 minutes)
- 6. Perform gonioscopy
- 7. Perform pachymetry (contact)
- 8. Perform specular microscopy (non-contact)
 - Non-contact specular microscopy can be performed anytime during the site visit and does not need to follow the order as written.
- 9. Perform anterior chamber OCT
- 10. Measure IOP at 10:00 a.m. (±30 minutes)
- 11. Measure IOP at 4:00 p.m. (±30 minutes)
- 12. Perform dilated funduscopic examination
- 13. Collect TRAVATAN Z from the study patients

